We now require estimates of the various quantities. Let us first suppose that we shall be selecting a fairly high risk group for the trial, with a minimum annual incidence of five per thousand and an average annual incidence of seven per thousand. Thus $I=0.007$. From a recently published overview, we have estimates $\lambda_1=0.49$ and $S=0.96$ [28]. Five-year survival from lung cancer in the UK has been reported as 6% [29], corresponding to $\lambda_3=0.56$. Henschke et al [30] report 85% 10-year survival of 412 stage I screen-detected cases. Assuming that the 72 screen-detected cases in their series with stage II or worse disease had zero ten-year survival, this would give an overall ten-year survival of 72%. Hypothesising further that this is artificially high as a result of length bias/overdiagnosis, we assume a ten-year survival of 50%. Thus we are estimating the effect of screening on mortality from the 'real', life-threatening tumours, rather than inflating the incidence of the intervention group and retaining the very high survival rate. This gives $\lambda_2=0.07$. We assume an uptake rate of 80%, which seems high but reflects the motivated nature of this group, already demonstrated by their positive response at two stages of approach.

WALD Single Screen Design

The resulting estimates of cumulative lung cancer mortality are shown in Table 1, adjusted for the 80% compliance. The Table also shows the relative risks of lung cancer death, and the numbers required per group (assuming equal group size) for 90% power to detect the difference as significant, with 2-sided testing at 5% level. The optimum time of analysis would be at the end of three years, and 16,000 subjects per group would be required (32,000 in all). The time to the result, taking into account the recruitment period, would be more likely to be around five years.

Year	Cumulative lung cancer mortality (study)	Cumulative lung cancer mortality (control)	RR (intervention vs control)	Number required per group
1	1.0	1.2	0.83	368,000
2	3.1	4.0	0.78	63,000
3	5.3	7.8	0.69	16,000
4	9.2	12.1	0.76	20,000
5	13.4	16.7	0.80	21,000
6	17.9	21.4	0.83	24,000

Annual screening for three years

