The calculations of the expected incidence of screen-detected and symptomatic tumours in the intervention group are similar to those for the single screen design, although now there is a mix of screen-detected and symptomatic tumours in the first three years. The cumulative mortality, relative risks and numbers required for 90% power are shown in Table 2.

The optimum power is achieved at 5 years, with 7,000 per arm. One might expect to add one year to this for recruitment.

Year	Cumulative lung cancer mortality (study)	Cumulative lung cancer mortality (control)	RR (intervention vs control)	Number required per group
1	1.0	1.2	0.83	368,000
2	2.8	4.0	0.69	35,000
3	5.0	7.8	0.65	13,000
4	7.8	12.1	0.64	8,000
5	11.2	16.7	0.67	7,000
6	15.2	21.4	0.71	7,200

Allowing for the 80% compliance rate, the single screen arm would incur screening costs for 12,800 CT scans (80% of 16,000). The 3-screen study would incur 16,800 scans (80% of 3 x 7000). Thus it would seem that the single-screen design, based on an idea by [name], would be more economical and would return an answer to the basic question earlier. We therefore propose a single screen in the study group vs usual care in the control group, with 16,000 subjects per group. We are aware that this design is not entirely conventional and that in a service screening programme, repeated screening would apply. Also, it has implications for analysis and interpretation (see below). However, in addition to its cost-effectiveness as a design, it has a number of other benefits.

The modelling has been carried out varying the parameters, and the single screen design has generally been more cost-effective. Also, the estimation of mortality from the rather simple semi-deterministic model above has been checked against a full stochastic model and results were in agreement.

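### Protocol 15.2: the tabulated mortality rates, the stated 90% power and the group sizes in Tables 1 and 2 are mutually inconsistent; 16,000 per group gives about 79% power at the printed year-3 rates

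*Protocol*

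**What the plan says.** Section 15.2 gives cumulative lung cancer mortality by year for the single-screen design (Table 1) and for three annual screens (Table 2), with a relative risk and a number per group in each row.

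- Table 1: the group sizes are those needed "for 90% power to detect the difference as significant, with 2-sided testing at 5% level", "assuming equal group size". The rates are said to be already adjusted for 80% compliance.
- Year-3 row of Table 1 (study, control, RR, number): "5.3 7.8 0.69 16,000".
- Design choice: "The optimum time of analysis would be at the end of three years, and 16,000 subjects per group would be required (32,000 in all").
- Table 2: "The cumulative mortality, relative risks and numbers required for 90% power are shown in Table 2". Its year-5 row is "11.2 16.7 0.67 7,000", and 7,000 per arm is taken as the optimum.
- Stated model inputs: incidence I = 0.007 (average; 0.005 is given as the minimum), λ1 = 0.49, S = 0.96, λ2 = 0.07, λ3 = 0.56, uptake 80%.

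The section then compares 12,800 scans (single screen) with 16,800 (three screens) using these group sizes.

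**The concern.** Rates, power, significance level, sidedness and allocation are all printed, so the group size follows from them. It comes out well above the tabulated figure in every row that can be judged. The main trial's 32,000 participants rest on the year-3 row. At the printed rates the chance of missing the assumed effect is about 21%, not 10%. The scan comparison and the statement that three years is the optimum time of analysis use the same columns.

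**Working it through.** **Inputs.** Rates and group sizes from Tables 1 and 2; 90% power, two-sided 5% and equal groups from the text above Table 1. I assume that the rates are per 1,000 (no unit is printed, but the incidence inputs imply it) and that the two-sided 5% level also applies to Table 2.

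**Formula.** n per group = (1.960 + z)² × [p1(1−p1) + p2(1−p2)] / (p1−p2)². The first factor is 10.507 for 90% power and 7.849 for 80%.

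**1. Trying to reproduce 16,000 (Table 1, year 3).** p1 = 0.0053, p2 = 0.0078; variance sum 0.005272 + 0.007739 = 0.013011; difference squared 0.0025² = 0.00000625.
- 90%: 10.507 × 0.013011 / 0.00000625 = 21,874.
- 80%: 7.849 × 0.013011 / 0.00000625 = 16,340.
- Power at 16,000: SE = √(0.013011/16,000) = 0.000902; 0.0025/0.000902 = 2.772; 2.772 − 1.960 = 0.812, so 79.2%.

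**2. Table 2, year 5.** For 11.2 versus 16.7, 90% needs 9,551 and 80% needs 7,134; power at 7,000 is about 79%.

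**3. Years 2 to 6 of both tables.** The last column multiplies the printed rates by 1.4, which is 0.007/0.005.

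| Table, year | Stated n | n for 90% | n for 80% | Power at stated n | n for 90%, rates × 1.4 |
|---|---|---|---|---|---|
| 1, 2 | 63,000 | 91,770 | 68,551 | 77% | 65,455 |
| 1, 3 | 16,000 | 21,874 | 16,340 | 79% | 15,582 |
| 1, 4 | 20,000 | 26,323 | 19,663 | 81% | 18,720 |
| 1, 5 | 21,000 | 28,600 | 21,364 | 79% | 20,302 |
| 1, 6 | 24,000 | 33,042 | 24,682 | 79% | 23,411 |
| 2, 2 | 35,000 | 49,444 | 36,934 | 78% | 35,268 |
| 2, 3 | 13,000 | 17,040 | 12,729 | 81% | 12,139 |
| 2, 4 | 8,000 | 11,191 | 8,359 | 78% | 7,960 |
| 2, 5 | 7,000 | 9,551 | 7,134 | 79% | 6,782 |
| 2, 6 | 7,200 | 9,816 | 7,332 | 79% | 6,958 |

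Year 1 is rounded too coarsely to judge.

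**4. Rounding and method.** Moving both year-3 rates by up to 0.05 per 1,000 gives 75.8% to 82.2% power at 16,000. Other methods for 90% give 22,024 (Poisson), 22,299 (log relative risk), 21,527 (Schoenfeld) and 22,061 (Freedman); one-sided 5% gives 17,831. None gives 16,000.

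**5. Which incidence lies behind the columns.** The control formula, I × Σ(1 − e^(−0.56(i−0.5))), gives in years 1 to 6, per 1,000:
- I = 0.005: 1.22, 4.06, 7.83, 12.13, 16.72, 21.49
- I = 0.007: 1.71, 5.69, 10.96, 16.98, 23.41, 30.09
- printed: 1.2, 4.0, 7.8, 12.1, 16.7, 21.4

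The printed column matches 0.005, not the stated 0.007.

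**6. The stated model at I = 0.007, year 3.** I read I_r as cumulative, I × r × (1 − PS), as the text describes it.
- Detected at screen: P = 0.007 × 0.96 / 0.49 = 13.714 per 1,000; deaths 13.714 × (1 − e^(−0.21)) = 2.598.
- Symptomatic cancers in years 1 to 3: 1.554, 3.748, 5.039 per 1,000; deaths with weights 0.753, 0.568, 0.244 total 4.531.
- Attenders: 2.598 + 4.531 = 7.129. Study arm: 0.8 × 7.129 + 0.2 × 10.961 = 7.896.
- 7.9 versus 11.0 per 1,000, RR 0.72; about 20,900 per group for 90%; 81.0% power at 16,000.

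Power at 16,000 in years 2 to 6 is 57.9%, 81.0%, 86.5%, 85.9% and 82.2%. The smallest group size for 90% falls in year 4, at about 17,900.

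**The case against.** The strongest reply is that the group sizes may be sound for 90% power and the mortality columns wrong. At the stated I = 0.007 the control formula gives about 1.4 times the printed column. The printed rates multiplied by 1.4 give 89% to 92% power at the stated sizes in years 2 to 6. Over those ten rows this reading fits as well as 80% power at the printed rates (mean absolute error 3.3% for both), and it is closer for year 2 of both tables and year 4 of Table 2. A reader might therefore infer from the match with 80% that the power was simply mislabelled. The protocol does not support so firm a diagnosis.

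The reply does not rescue the 90%. It concedes that the mortality columns contradict the stated incidence. At year 3 it also needs the printed ratio of about 0.68 (5.3/7.8; the table prints 0.69), whereas the protocol's formulas give 0.72.

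A reader might also infer that the funding decision rests on this power. The protocol summary says that pilot screening data go to the funder's review, and the criteria in section 15.4 are recruitment, compliance, centre workload and the database. Power is not among them, and the pilot's size is unaffected.

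**Conclusion.** Wrong as written. The printed rates, the 90% power and the group sizes cannot all be right. At the printed rates 16,000 per group gives about 79% at year 3 (about 21,900 needed for 90%), and 7,000 per arm gives about 79% in Table 2 at year 5 (about 9,550 needed). On the stated inputs 16,000 gives about 81% at year 3 and at most about 86.5% in any of the six years, so 90% is not reached either way. Whether the slip lies in the power or in the incidence behind the columns is open.

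This rests on reading the rates as per 1,000, a two-sided 5% two-proportion comparison, and, for the model figures, a cumulative I_r. The preference for a single screen on scan numbers survives at the printed rates: at 90% the comparison becomes about 17,500 (0.8 × 21,874) against about 22,900 scans (0.8 × 3 × 9,551).

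**What to change.** - State which annual incidence underlies each column of Tables 1 and 2.
- Regenerate mortality, relative risk and number per group in both tables from one set of inputs and one power. The incidence question and the year-3 row of Table 1 concern the same columns and should be settled in the same revision.
- Replace the 90% with the power that 16,000 per group delivers at year 3: about 79% if the printed rates stand, about 81% from the stated model at I = 0.007. Relabelling to 80% alone would leave columns that contradict the stated incidence.
- Redo the optimum-year statement (the stated model points to year 4) and the scan comparison on the corrected basis.

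This is a change of text and tables. Restating the figure adds no participants; the cost is a less favourable stated power. Keeping 90% at year 3 would mean about 21,900 per group on the printed rates, or about 20,900 on the stated model.

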14.1 Schedule for Follow-up

Once a participant has been randomised onto the UKLS trial they will be followed up for a period of 10 years. Follow-up information on all participants will be collected indirectly through either Cancer Registry or via The Office of National Statistics (ONS). A subset of participants will be contacted to complete the Psychosocial and Health Economics questionnaires.

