as shown by Paci and Duffy [26]. Launoy and colleagues [27] have shown that in a programme with a screening interval of r years, the expected proportion of tumours in those attending which are screen-detected is:

$$PS = \frac{S(1 - e^{-\lambda_1 r})}{\lambda_1 r(1 - (1 - S)e^{-\lambda_1 r})}$$

It follows that the cumulative rate of symptomatic cancers arising in the r years after a screen years will be:

$$I_r = I(1 - PS)$$

The number of symptomatic cancers arising in the first year after a screen is I_1 . The number arising in the r th year ($r=2,3,4\dots$) after a screen is $I_r - I_{r-1}$. In the control group, and in those who elect not to be screened in the study group, the annual rate of symptomatic cancers is I .

The cumulative rate of lung cancer death by the end of year r from asymptomatic tumours diagnosed in the intervention group at the single screen at the beginning of the study is estimated as:

$$D_1 = P(1 - e^{-\lambda_2 r})$$

The corresponding cumulative death rate in the control group is estimated as:

$$D_0 = I \sum_{i=1}^r (1 - e^{-\lambda_3(i-0.5)})$$

This uses the approximation of time of diagnosis as the midpoint of the relevant year. For the symptomatic tumours arising after the screen in the intervention group, the expected cumulative death rate is:

$$D_0 = \sum_{i=1}^r (I_j - I_{j-1})(1 - e^{-\lambda_3(r-j+0.5)})$$

where we define I_0 as 0.

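### Years 2 and 3 of Table 1 do not follow from the protocol's own mortality model; the optimum is year 4 (flat to year 5), where 16,000 per group gives about 85–87% power, not 90%

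*Protocol*

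**What the plan says.** Section 15.2 sets out a deterministic model for cumulative lung cancer mortality in the two arms. It assumes a target population "with a minimum annual incidence of five per thousand and an average annual incidence of seven per thousand", and takes 0.007 as the working incidence. Table 1 lists, by year, the cumulative mortality per arm, the relative risk and the number per group "for 90% power to detect the difference as significant, with 2-sided testing at 5% level". The year-3 row reads 5.3 (study), 7.8 (control), RR 0.69 and 16,000 per group. From it the protocol concludes: "The optimum time of analysis would be at the end of three years". It puts the time to result, with recruitment, at around five years.

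Table 2 does the same for three annual screens. It finds the best power at year 5 with 7,000 per arm and says "One might expect to add one year to this for recruitment". The protocol then compares 12,800 scans with 16,800 and concludes that the single screen "would be more economical and would return an answer to the basic question earlier".

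**The concern.** The printed study-arm column is not smooth. Its yearly increments are 1.0, 2.1, 2.2, 3.9, 4.2 and 4.5, against 1.2, 2.8, 3.8, 4.3, 4.6 and 4.7 in the control arm. The within-year rate ratio is therefore 2.2/3.8 = 0.58 in year 3 and 3.9/4.3 = 0.91 in year 4. A model built from constant exponential rates should not jump like that.

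The year-3 row is where the 16,000, the stated 90% power and the three-year optimum all come from. It also feeds both grounds for preferring one screen to three, namely fewer scans and an earlier answer.

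**Working it through.** **Inputs (section 15.2).** λ1 = 0.49, S = 0.96, λ2 = 0.07, λ3 = 0.56, uptake 80%, two-sided 5%, 90% power, equal groups. The stated incidence is I = 0.007.

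**Model.**
- Screen-detected: P = IS/λ1, with deaths by year r of P(1 − e^(−λ2 r)).
- Symptomatic after the screen: Σ (I_j − I_(j−1))(1 − e^(−λ3(r−j+0.5))).
- Control: I Σ (1 − e^(−λ3(i−0.5))).
- Study arm: 0.8 × screened + 0.2 × control.

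**The symptomatic-cancer formula.** The text calls I_r cumulative ("It follows that the cumulative rate of symptomatic cancers arising in the" r years after a screen) but prints I_r = I(1 − PS), without a factor r. Used literally at I = 0.007, it gives RR about 0.53 and n about 6,700 at year 3, with n still falling (about 3,500 at year 4). The tables were not made that way. I used two cumulative forms: (A) I_r = rI(1 − PS), and (B) I_r = Ir − P(1 − e^(−λ1 r)).

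**Reproducing the control column.** At I = 0.005 the model gives 1.22, 4.06, 7.83, 12.13, 16.72 and 21.49, against the printed 1.2, 4.0, 7.8, 12.1, 16.7 and 21.4. At I = 0.007 these values would be 1.4 times larger, so the mortality columns appear to use 0.005.

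**Year 3 worked through (form A, I = 0.005, per 1,000).**
- P = 5 × 0.96/0.49 = 9.796; deaths 9.796 × (1 − e^(−0.21)) = 1.856.
- PS = 0.778, 0.621, 0.508, so I_1 to I_3 = 1.110, 3.787, 7.386, with increments 1.110, 2.677, 3.599.
- Symptomatic deaths: 1.110 × 0.753 + 2.677 × 0.568 + 3.599 × 0.244 = 3.24.
- Study arm: 0.8 × (1.856 + 3.237) + 0.2 × 7.83 = 5.64. RR = 5.64/7.83 = 0.72.

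**All years, study arm at I = 0.005:**

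| Year | Printed | Model (A–B) | Printed RR | Model RR |
|---|---|---|---|---|
| 1 | 1.0 | 0.99–1.01 | 0.83 | 0.81–0.83 |
| 2 | 3.1 | 2.86–2.91 | 0.78 | 0.70–0.72 |
| 3 | 5.3 | 5.64–5.69 | 0.69 | 0.72–0.73 |
| 4 | 9.2 | 9.16–9.21 | 0.76 | 0.76 |
| 5 | 13.4 | 13.25–13.29 | 0.80 | 0.79 |
| 6 | 17.9 | 17.73–17.76 | 0.83 | 0.82–0.83 |

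Years 1 and 4–6 agree to within about 0.2 and with similar RRs. Years 2 and 3 miss in opposite directions.

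**Where 16,000 comes from.** Use n = [1.960√(2p̄(1−p̄)) + 1.282√(p1(1−p1) + p2(1−p2))]²/(p1 − p2)². The printed 5.3 and 7.8 per 1,000 give about 21,900. Multiplied by 7/5 to the 0.007 scale, they give about 15,600. So the n column matches I = 0.007 roughly, and 16,000 rests on the 5.3.

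**Corrected n and power at I = 0.007 (A–B):**

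| Year | n per group, 90% power | Power with 16,000 |
|---|---|---|
| 3 | 20,900–22,000 | 79–81% |
| 4 | 17,900–18,600 | 85–86% |
| 5 | 18,200–18,700 | 85–86% |
| 6 | 20,200–20,600 | 82% |

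Form A at year 4 is 86.5%, hence 85–87% in the text. No year reaches 90%. Year 4 is also the minimum at I = 0.005 and without the uptake adjustment. In a sweep of the parameters, year 3 became the minimum only at λ1 = 0.8. With λ2 = 0.07 and S = 0.96 that needs about 28,000 per group.

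**Comparison with three screens (Table 2 as printed).**
- Scans: 0.8 × 17,929 = 14,343 to 0.8 × 18,583 = 14,866, against 0.8 × 3 × 7,000 = 16,800. The saving is 11–15%. The protocol's is 1 − 12,800/16,800 = 24%.
- A year-3 analysis with 90% power would need 0.8 × 20,880 = 16,704 to 0.8 × 21,991 = 17,593 scans, which leaves no real saving.
- Timing: around five years with a year-3 optimum implies about two years of recruitment. Then 4 + 2 = 6, against 5 + 1 = 6.

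**The case against.** Several defences stand in part.

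- **No analysis time is fixed.** Year 3 is an optimum under a model. Section 15.5 says that a full analysis plan is in development, and section 14.1 states "Once a participant has been randomised onto the UKLS trial they will be followed up for a period of 10 years". A reader might infer that the trial is committed to a three-year analysis, or will drift to an underpowered ten-year one. The protocol supports neither. Section 15.5 also foresees dilution under a single screen and adds an analysis of the hazard ratio over time.
- **The timing advantage narrows; it does not vanish.** From randomisation it is still year 4 against year 5. The tie at six years rests on loose recruitment remarks, one of them inferred.
- **The economy claim survives in reduced form.** Multiplying the printed year-4 n of 20,000 by 0.8 suggests a saving of only 5%, but that mixes a printed n with a corrected optimum.
- **The design case is I = 0.007.** Power at 0.005 would be lower (65–67% at year 3), but 0.005 is the minimum incidence, not the planning value. Its apparent use in the mortality columns is a separate inconsistency.
- **The missing r is a slip in print.** The tables were not computed with it.
- **Stochastic check.** Section 15.2 reports agreement with a full stochastic model but gives no figures. This cannot support a row that the deterministic model itself does not yield.

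The three-screen equations are not printed, so agreement with Table 2 needs a reconstruction. A continuous-time version gives 4.99, 7.73, 11.10 and 15.05 at years 3–6, against 5.0, 7.8, 11.2 and 15.2. I treat that as supporting evidence only.

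**Conclusion.** The point holds. The year-2 and year-3 study-arm values in Table 1 do not follow from the stated model, and the quoted sample size, power and optimum rest on the year-3 value. At the stated incidence, analysing at year 3 instead of year 4 costs about 6 percentage points of power, and the shortfall against the claimed 90% is about 9–11 points at year 3 and 3–5 at years 4–5. The choice of a single screen is weakened but not overturned.

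This rests on the protocol's own parameters, on reading I_r as cumulative, on a standard two-proportion calculation, and on Table 2 as printed. Years 4 and 5 differ by less than 2% in n, so the documents do not show that a primary analysis at exactly four years is required.

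**What to change.** In section 15.2:

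1. Correct the year-2 and year-3 rows of Table 1 (about 2.9 and 5.6–5.7 on the 0.005 scale) and their RRs and n.
2. Use one incidence for the mortality and n columns, and apply it to Table 2 as well.
3. Print the cumulative rate as rI(1 − PS).
4. State the optimum as year 4, flat to year 5, and the power of 16,000 per group as about 85–87% there and about 80% at year 3.
5. Reword the claims of an earlier and more economical answer: year 4 against year 5 from randomisation, about six years each with recruitment, and a scan saving of about 11–15%.

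The cost is a less favourable stated power and an optimum about one year later. The target of 32,000 can stay if that power is accepted. Keeping 90% would instead need about 17,900–18,700 per group (35,800–37,400 in all), above the maximum of 32,000 in the protocol summary.

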15.3 Interim Monitoring and Analyses

Formal interim analyses of the accumulating data will be performed at regular intervals (at least annually) for review by an Independent Data Monitoring and Safety Committee (IDSMC). These analyses will be performed at the LCTU. The IDSMC will be asked to give advice on whether the accumulated data from the trial, together with results from other relevant trials, justifies continuing recruitment of further patients or further follow-up. A decision to discontinue recruitment, in all patients or in selected subgroups will be made only if the result is likely to convince a broad range of clinicians including participants in the trial and the general clinical community. If a decision is made to continue, the IDSMC will advise on the frequency of future reviews of the data on the basis of accrual and event rates. The IDSMC will make recommendations to the Trial Steering Committee (TSC, see section 16) as to the continuation of the trial.

15.4 Criteria to proceed from pilot trial to main trial

The crucial factors are the proportion of the initial sample approached that are successfully recruited, the compliance with screening of those randomised to the intervention, and the ability of the centres to cope with the screenees. We propose continuation criteria for each of these in turn, in each case with three possible outcomes: (1) proceed with the main trial as originally envisaged; (2) revise the protocol of the main trial to correct for problems observed in the pilot, and then proceed; and (3) abandon the main trial and follow up the pilot population, for synthesis of their results with those of other European trials.

A. For recruitment, we propose the following criteria for actions (1), (2) and (3) respectively.

1. If recruitment is more than 90% of the 4.9% anticipated, proceed to main trial.
2. If recruitment is 50-89% of the 4.9% anticipated, revise protocol to include, either an expansion of the initial approached population or to include a second contact of non-responders to first approach, or both. Then proceed to main trial as amended.
3. If recruitment is less than 50% of the 4.9% anticipated, abandon the plan for the main trial.

B. For compliance with screening (CT study group) or usual care (Control group), we propose:

1. If compliance is 75% or more, proceed to main trial.
2. If compliance is 50-74%, revise protocol to increase total study size or to make attendance for screening easier or more attractive, or both. Then proceed to main trial as amended.
3. If compliance is less than 50%, abandon the plan for the main trial.

C. Ability of the centres to cope with the screening workload:

1. If centres screen 80% or more of those scheduled within the anticipated time, proceed to main trial.
2. If centres screen 50-79% of those scheduled within the anticipated time, revise protocol to increase the number of centres or enhance support offered to centres or both. Then proceed to main trial as amended.
3. If centres screen less than 50% of those scheduled within the anticipated time, abandon the plan for the main trial.

We do not propose to use the numbers recommended for further diagnostic workup as a criterion to proceed or not, but if the numbers exceed 30% in either centre, we propose to revise the protocol in terms of training and quality control for initial screening.

D. UKLS Database

Successful implementation of the UKLS database and information system in the LCTU, and recruitment centre clinics in both pilot centres as well as the CT Review Centre. Questionnaire, epidemiological and clinical data collection successfully uploaded onto the UKLS database. An earlier version of this database has been used to manage the NELSON trial, thus no major issues are envisaged, which cannot be resolved.

